Obesity (a body mass index ≥ 30 and waist to hip ratio of at least 0.9 in males and at least 0.85 in females) has been correlated with higher mortality risk and is associated with a proinflammatory state (e.g. elevated levels of TNF-alpha and interleukin-6). Obesity has also been associated with a lower immune response to various types of vaccination (e.g. influenza, hepatitis B, tetanus). As the prevalence of obesity increases, so does the need for a deeper mechanistic understanding of how obesity attenuates vaccination response. It is important to assess the effect of obesity on the immune response to vaccines. The pneumococcal polysaccharide vaccine (Pneumovax 23) is a safe method for stimulating an immune response and its effect on obesity has not been elucidated. As a growing population of obese individuals inevitably age and become susceptible to pneumococcal infections, it is important to consider how obesity may impact the efficacy of Pneumovax 23. We hypothesize that a chronically stressed immune system in obese individuals will be unable to respond as well to vaccination compared to individuals with a BMI between 22 and 25. We will utilize a prospective cohort design. We will also conduct various surveys to examine psychosocial factors that may influence the interaction between obesity and immune response to vaccination. We will also perform genotyping of STING to assess how it may influence the relationship between obesity and immune response to vaccination.

2. HYPOTHESIS AND SPECIFIC AIMS:

The primary objective of this study is to demonstrate the effect of obesity on the immune system's ability to mount a protective immune response against the Pneumococcal Polysaccharide Vaccine (Pneumovax 23).

Primary Hypothesis (stated as null): Levels of antibodies to serotypes in Pneumovax 23 in pre- and post- vaccination in individuals with a BMI between 22 and 25 and obese individuals are identical.

Secondary Hypothesis (stated as null): Levels of pro- and anti-inflammatory cytokine levels pre- and post-vaccination in individuals with a BMI between 22 and 25 and obese individuals are identical.

Tertiary Hypothesis (stated as null): The perceived level of stress, loneliness, social support, and dispositional optimism will be the same between the group of individuals with a BMI between 22 and 25 and the group of obese individuals, or between groups with different immune responses to the vaccine.

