Quaternary Hypothesis (stated as null): Those who carry *STING* variants and those who are wildtype *STING* carriers will not have differing immune responses to Pneumovax 23.

Specific Aim 1: Quantify changes in the adaptive immune response to Pneumovax 23 by measuring specific antibodies to Pneumovax 23 antigens pre- and post-vaccination in the group of individuals with a BMI between 22 and 25 and the group of obese individuals.

Specific Aim 2: Quantify changes in the inflammatory immune response to Pneumovax 23 by measuring C-reactive protein (CRP) and cytokines pre- and post-vaccination in the group of individuals with a BMI between 22 and 25 and the group of obese individuals.

Specific Aim 3: Determine if perceived stress, loneliness, social support, and dispositional optimism are associated with adaptive immune response to Pneumovax 23.

Specific Aim 4: Determine how *STING* genotypes may affect the adaptive immune response to Pneumovax 23.

3. BACKGROUND AND SIGNIFICANCE:

Pneumococcal infections are a leading cause of adult and childhood hospitalization and mortality with an estimated 1.6 million deaths occurring annually.^{1,2} Prophylactic measures against pneumococcal infections exist in the form of a vaccine called Pneumovax 23. While Pneumovax 23 is approved for use in all adults 50 years or older and individuals as young as 2 years who are at increased risk for infection, the vaccine is recommended for all adults 50 years and older or adults age 19 to 64 with conditions or treatments that affect the immune system.³ These recommendations were developed, in part, from a 14-year cohort study comparing the proportion of pneumococcal infections caused by varying pneumococcal serotypes included in vaccinated and unvaccinated individuals.⁴ Pneumovax 23 had an overall efficacy rate of 57% in preventing pneumococcal infection. In addition to recommending the vaccine to the elderly, the vaccine is also recommended for individuals who have been identified as being at higher risk for contracting pneumococcal pneumonia, such as those infected by human immunodeficiency virus.⁵ Increased weight gain and a high body mass index have been associated with an increased risk for contracting pneumococcal pneumonia, suggesting it is desirable to provide effective vaccination of this susceptible population.⁶

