At the end of the screening, we will request an email address in order to email a copy of the consent form for the participant to review before the first visit, during which the consent form will be reviewed with the participant and any questions addressed. We will also request a cell phone number at which we can text participant reminders the night before their appointments (visit 1 and visit 2). If the participant declines a reminder text, we will have a reminder phone call, if they decline this, we will send email reminders.

Consenting: Upon arriving the co-investigators will have a discussion with the participants about the study. Any questions or concerns will be appropriately addressed. All co-investigators obtaining consent will be trained on obtaining informed consent through the CTS800 CTSI Informed Consent Training. [name] will provide supervision.

Confirmation of Screening Accuracy: During the first visit, a pregnancy test will be given to females and an HbA1C will also be taken via finger prick to assess blood sugar levels. If the participant is not pregnant and has an HbA1C less than 6.5%, then comprehensive physical exams will be performed and vitals will be taken to assess health. If the participant is found to be pregnant, to have an HbA1C greater than 6.5%, to have a positive physical exam or comprehensive past medical history finding the participant will be considered a “screening failure”. Vials from the blood draw will be sent to Shands for a CBC and CMP. If there is a clinically significant CBC or CMP finding as determined by [name], then the participant will be considered a “screening failure.” CBC/CMP values are being considered because these values will impact the conclusions we can draw from the data. These values are not necessary to determine if there are any contraindications to the vaccine. If screening failure occurs, then the participant will be ineligible to continue with the study based off of failure to meet inclusion criteria.

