2. Study Design: Participants will be asked to fast after midnight prior to the first blood draw. A baseline blood draw (39 mL) will be performed for each participant. Pneumovax 23 will then be administered into the deltoid muscle by the CRC nurses; needle length will be adjusted according to distance from skin surface to muscle bundle. The Pneumovax 23 vaccine will be provided by the University of Florida Investigational Drug Services. They receive their commercial products from McKesson Pharmaceuticals. Effort will be taken to ensure that all participants receive the same lot number of Pneumovax 23.

Blood will be drawn 4-6 weeks following vaccination, as primary antibody production peaks during this time frame.⁴⁰ At that time, a total of 33 mL of blood will be drawn for analyses of antibody and cytokine levels. Table I illustrates what assays will be performed on the blood drawn at each time point and Table II illustrates the schedule of each blood draw. Figure 2 outlines a progression of events that will occur during both the screening and the first visit.

[figure not shown]

Figure 2. Progression of events during Visit 1:
Consenting, screening confirmation, blood draw,
vaccination, survey administration, and payment distribution

B. Measurements to be Collected

1. Basic Demographics (e.g. gender, age, race, ethnicity, education, etc.) will be collected.
2. Height, weight and hip-waist circumference will be collected.
3. Baseline Characteristic Assessments: Pregnancy will be evaluated by urine test, and hemoglobin A1C level will be determined with a portable finger-prick monitor.
4. Whole Blood Lab Assays: The following whole blood lab assays will be sent to and performed by Shands Laboratory: total IgG titers, complete metabolic panel, erythrocyte sedimentation rate, and complete blood count (CBC).
5. Anti-pneumococcal Antibodies: IgG antibody titers specific for each serotype in Pneumovax 23 (i.e. 1, 2, 3, 4, 5, 6B, 7F, 8, 9N, 9V, 10A, 11A, 12F, 14, 15B, 17F, 18C, 19F, 19A, 20, 22F, 23F, and 33F) will be analyzed using a panel ordered through the Mayo Clinic.
6. Serum Analyte Measurements: ELISA will be used to measure various acute phase reactants (e.g. TNF, C reactive protein, interferons, interleukins, etc.) and Ig subclasses. If significant

differences are not observed between arms then a cytometric bead assay may be employed. ELISAs will be performed in [name] lab.

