 - a. Inability to fast for 8 hours prior to the initial blood draw
4. Immunization
 - a. Immunized with Pneumovax 23
 - b. Immunized with Prevnar
5. Medications
 - a. Currently taking any of the following medications or within the 4 weeks of study:
 - i. Immunosuppressive drugs or chemotherapeutic agents including azathioprine, mycophenolate mofetil, TNF inhibitors, cyclosporine, methotrexate, leflunomide, cyclophosphamide, sulfasalazine, antimalarial drugs, chlorambucil, and nitrogen mustard.
 - ii. Steroids including prednisone, cortisone, and hydrocortisone.
6. A history of clinical illness, as determined by a comprehensive patient history at the first visit.
 - a. Pneumonia
 - i. Previously had Pneumonia
 - b. Low blood pressure
 - i. Experienced dizzy spells
 - c. Significant cardiovascular disease
 - i. Recently hospitalizations deemed significant at the discretion of the Principal Investigator
 - ii. History of heart attack
 - iii. History of stroke
 - d. Spleen
 - i. Splenectomy
 - ii. Damage to spleen
 - e. Lung Disease
 - i. History of lung disease
 - f. Kidney disease
 - i. Blood in urine
 - ii. Protein in urine
 - g. Liver disease
 - i. Previous or current liver diseases including hepatitis A, B, or C, liver cirrhosis, or autoimmune hepatitis
 - h. Leukopenias
 - i. Hemoglobinopathies
 - i. History of sickle cell disease, thalassemia
 - j. HIV/AIDS
 - i. History of HIV infection

- k. Recreational IV drug use
 - i. IV drug use is a risk factor for HIV infection, which may change the immune response to Pneumovax23.
- l. History of idiopathic thrombocytopenic purpura
- m. History of chronic inflammatory diseases including rheumatoid arthritis or chronic granulomatous disease
- n. Autoimmune disease
- o. Immunodeficiencies
 - i. e.g. neutropenia, common variable immune deficiency, Bruton's X-linked agammaglobulinemia; SCID; Selective IgA deficiency; Wiskott-Aldrich Syndrome; Ataxia Telangiectasia; DiGeorge Syndrome; Chronic Granulomatous Disease; Hyper IgE Syndrome; Complement deficiencies

7. Weight

- a. Planning on losing weight within the time frame of the study
- b. Have experienced excessive weight loss or gain within two months prior to the study
- c. Planning to undergo liposuction, gastric bypass, stomach stapling, whipple procedure, or reconstructive surgery involving transplantation of adipose tissue within the study period
- d. Bodybuilder or someone who takes part in excessive weight training

8. Allergy

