7. TIME AND EVENTS

Potential participants will be screened via phone or REDCap surveys. If a potential participant qualifies after the screening survey, a visit to the UF campus CRC building will be scheduled.

Upon arrival at the CRC, informed consent will be reviewed, and the informed consent document will be signed. Following this enrollment, the participant will have vitals checked and will undergo an HbA1C fingerprick test, a urine pregnancy test, a physical exam, and a comprehensive medical history. If the participant still meets inclusion criteria, then screening accuracy is confirmed. Participants who are found to be screening failures will be told they are no longer eligible for the second part of the study and be given a gift card. For those that continue, blood will be drawn and sent to respective locations outlined in Table 1. Subsequently, the Pneumovax 23 vaccine will be administered. Following administration of the vaccine, four questionnaires will be administered; simultaneously while completing the forms, the

participant will be monitored for adverse side effects to the vaccine. Payment will be administered after the surveys, and the subsequent visit will be scheduled.

At the second visit 4-6 weeks following the first, blood will be drawn once more and distributed to the locations outlined in Table 1. After the blood draw, the participant will be compensated and thanked profusely for participating in the study. Completion of visit two marks the culmination of the study for that particular participant. Data analysis will ensue once 56 participants have progressed through the study. The events occurring in the study are outlined in Table 3.

Table 3. Proposed Schedule

	Events	Prior to Visit 1	Estimated Time (min)	Visit 1: Day 0	Visit 2: Wk 4-6
Screening	Contact with participants by phone or email	X	10		
	Set up REDCAP and chart for each participant	X	20		
	Screening via phone or REDCAP survey	X	10		
	Instructions email or phone call	X	10		
Visit 1	Informed Consent		20	X	
	Urine Pregnancy Test		10	X	
	A1C		5	X	
	Medical History		10	X	
	Physical Exam,		10	X	
	Waist/Hip Ratio		2	X	X
	Vitals		2	X	X
	Blood draw for CMP, CBC, and ESR		6	X	
	Pneumvax23 Vaccination		5	X	
	Blood draw for total IgG, serotypes, and cytokine assays		6	X	X
	Questionnaire Completion (4 surveys)		30	X	
	Instructions for next visit		5	X	
	Payment		5	X	X
	Total Time Per Visit (min)			114	20-30

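### CRP and cytokines are drawn fasted at Visit 1 but under no stated feeding condition at Visit 2, so any feeding effect would enter the within-group pre-to-post change of Aim 2

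*Protocol*

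**What the plan says.** Fasting appears in two places in the Protocol, each time tied to the first draw:

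- Section 4.A.2 (Study Design): "Participants will be asked to fast after midnight prior to the first blood draw".
- Exclusion criterion 3: "Inability to fast for 8 hours prior to the initial blood draw".

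The second draw is described without any condition on food. Section 4.A.2 says "At that time, a total of 33 mL of blood will be drawn for analyses of antibody and cytokine levels", and section 7 (Time and Events) says "At the second visit 4-6 weeks following the first, blood will be drawn once more and distributed to the locations outlined in Table 1". Table 1 lists cytokines and inflammatory markers at both visits. Table 3 has no fasting check at Visit 2.

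The two draws are then compared. Section 2 states: "Specific Aim 2: Quantify changes in the inflammatory immune response to Pneumovax 23 by measuring C-reactive protein (CRP) and cytokines pre- and post-vaccination". The secondary null hypothesis is that "Levels of pro- and anti-inflammatory cytokine levels pre- and post-vaccination in individuals with a BMI between 22 and 25 and obese individuals are identical".

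For analysis, Protocol 5.C specifies an ANCOVA of obese against non-obese participants adjusted for age and gender, with the remaining endpoints treated similarly. The SAP names only the antibody response as an outcome and gives no cytokine or CRP analysis. No section provides for recording time since the last meal, and the design limitations in 4.F do not raise the matter.

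**The concern.** A change score is interpretable when both measurements are taken under the same conditions. Here the baseline condition is fixed, strictly enough to exclude people who cannot meet it, and the follow-up condition is left open. If food moves any of these markers, that movement becomes part of the pre-to-post difference. The study has no unvaccinated arm in which it could be seen separately.

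At stake is the part of Aim 2 that describes how much the inflammatory markers change in each BMI group. The group comparison is better protected, because a shift common to both groups drops out. That protection depends on two things the plan does not secure: that obese and non-obese participants respond alike to food, and that similar shares of each group arrive fed at Visit 2.

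**Working it through.** **1. Conditions at the two draws**

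| | Visit 1 | Visit 2 |
|---|---|---|
| Fasting required | Yes (4.A.2; exclusion criterion 3) | Not stated (4.A.2, 5.A, 7, Tables 1 and 3) |
| Time since last meal recorded | Not stated | Not stated |
| Cytokines and inflammatory markers (Table 1) | Yes | Yes |
| CMP, and CBC with ESR (Table 1) | Yes | No |
| Blood volume | 3+3+3+5+15+10 = 39 mL | 3+5+15+10 = 33 mL |

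The volumes add up to the stated totals. They confirm that the cytokine tube is drawn at both visits and that only the CMP and CBC/ESR tubes are dropped at Visit 2.

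**2. Sample size used below**

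The plan expects 23 evaluable participants per group. From the titer table (Protocol 5.E; SAP Table 1), the means are 9.214 (BMI under 25, n = 14) and 7.429 (BMI over 25, n = 7). The difference is 1.786, the pooled SD 2.104, and d = 1.786/2.104 = 0.849. A two-sided t test at 0.05 with 80% power then needs 22.8, so 23 per group. The plan's figure reproduces. It relates to the antibody outcome and is used here only as the n.

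**3. Illustration of size (assumed inputs)**

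The documents give no feeding effect. Let f be the mean shift caused by feeding, in SDs of the within-person change, assumed to be 0.2, 0.3 or 0.5. Assume no true vaccine effect on the marker and two-sided α = 0.05. If only some participants are fed at Visit 2, f is the share fed times the effect in those fed. With f = 0, every rate below is 5%.

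- *(a) Change within one group, n = 23.* Paired t test, 22 df, noncentrality f√23 = 4.796f.
- *(b) Contrast in change, 23 per group, mean shifts differing by f.* Two-sample t test, 44 df, noncentrality f√(23/2) = 3.391f.
- *(c) Same contrast, same feeding effect f in both groups, share fed at Visit 2 differing by an assumed 30 points.* The mean shifts differ by 0.30f, so the noncentrality is 3.391 × 0.30f = 1.017f. Only the effect on the mean is counted.
- *(d) Same contrast, shift identical in both groups.* The shift cancels.

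| f | (a) within group | (b) shifts differ by f | (c) 30-point difference in share fed | (d) common shift |
|---|---|---|---|---|
| 0.2 | 15.1% | 10.2% | 5.5% | 5% |
| 0.3 | 28.0% | 16.9% | 6.0% | 5% |
| 0.5 | 63.0% | 38.2% | 7.9% | 5% |

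The t tests stand in for the age- and gender-adjusted ANCOVA; the adjustment set contains nothing that would remove a feeding effect.

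**The case against.** The strongest case on the other side has five parts.

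- *Visit 2 is not stated to be fed.* Correct. Table 3 schedules instructions about the next visit, and Protocol 4.A provides a reminder the night before each visit, but the content of neither is given. Consent pages are not in the text available and may carry an instruction. A reader might infer a systematic fasted-versus-fed comparison; the documents support only fasted versus unspecified.
- *Fasting may have been meant for the metabolic panel.* Table 1 places the CMP at Visit 1 only, and it is used to declare screening failures, so a one-time fast would fit. The Protocol gives no reason for the fast, so the exclusion criterion does not show that the authors thought fasting necessary for the inflammatory markers. The asymmetry remains, because the same visit supplies the cytokine baseline.
- *The planned inference is between groups.* This largely stands. The ANCOVA compares obese with non-obese participants, and Protocol 4.F describes relative differences between groups as the outcome of interest. A common shift cancels there. It does not cancel in the within-group change that Aim 2 sets out to quantify.
- *The feeding effect is assumed.* This stands. Nothing in the documents says that food moves CRP or any cytokine, so the table is a sensitivity illustration. A reader might also pool all 46 people in one pre-to-post test, which gives 26% to 91% over the same range of shifts, but the plan names no such test.
- *Matched fasting would not make the change attributable to the vaccine.* Also correct, since there is no unvaccinated arm. It would remove one avoidable source of difference and no more.

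A reader might further take the overnight instruction and the 8-hour criterion as contradictory. One is an instruction and the other a minimum ability for eligibility; a draw at 8 a.m. or later satisfies both.

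**Conclusion.** The point holds in a limited form. Followed as written, the plan gives a controlled baseline and an uncontrolled follow-up for CRP and cytokines, and it collects nothing that would show how far the two conditions differed. The within-group change in Aim 2 is directly exposed. The obese versus non-obese comparison is exposed only if the feeding effect or the share fed at Visit 2 differs between groups. If only the share fed differs, by 30 points, the inflation is slight; it becomes material only if the groups' mean shifts differ by something approaching the larger assumed values.

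All rates rest on an assumed shift of 0.2 to 0.5 SD, no true vaccine effect, and 23 evaluable participants per group. The actual bias is unknown and could be nil for a given marker.

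The documents do not support extending this to the main result. The primary outcome is antibody-based, and nothing in the documents suggests that fasting affects titers. This is an improvement worth making to a non-primary aim and does not threaten the study's principal conclusion.

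**What to change.** 1. In Protocol 4.A.2 and section 7, ask for the same fast before Visit 2 as before Visit 1, and put it in the Visit 2 reminder that is already planned.
2. Record time since last meal at both draws. Use it to check compliance and for a sensitivity analysis of the between-group comparison of CRP and cytokines. It should not be relied on to correct the within-group change: if most participants are fasted at Visit 1 and fed at Visit 2, time since last meal nearly coincides with visit, and no model can separate the two.
3. If Visit 2 draws are already complete, report within-group changes with a plain statement that the follow-up feeding state was not controlled, and rest inference on the between-group contrast.

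The cost is a line or two of protocol and reminder text, one extra data field per draw, and a small burden on participants at Visit 2. Every participant will already have passed the eligibility condition on ability to fast.

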7. The Perceived Stress Scale-10, which is a 10-item scale assessing how stressful participants perceive their lives to be. Scores range from 0 to 40. This scale has shown adequate reliability (alpha = 0.78).³²
8. The UCLA Loneliness Scale, a 20-item scale that measures subjective feelings of loneliness and social isolation. Scores range from 0 to 60. This scale has shown adequate reliability (alpha = 0.89 to 0.94) with one year test-retest reliability of $r = 0.73$.³³
9. The Interpersonal Support Evaluation List-12, a 12-item scale that measures perceived social support along 3 dimensions: appraisal support (availability of someone to talk to), belonging support (availability of people to do things with), and tangible support (e.g. material aid). Scores range from 0 to 36. This scale has shown adequate reliability (alpha = 0.88 to 0.90 in the general population).³⁴
10. The Life Orientation Test-Revised), a 10-item scale measuring optimism versus pessimism along a continuous scale.³⁵ Scores range from 0 to 40.
11. Genetic Sequencing: the human *STING* gene will be sequenced.

Protocol for Collection and Storage of Venous Blood

The blood volume will be distributed between Shands' Laboratory, the Mayo Clinic's Laboratory, and [name] to assess CMP, CBC, antibody responses, and perform experiments.

Table 1. Itemized Details of Laboratory Specimen Collection

Test	Amount Needed	Collection	Test Location	Location of Draw	Time of Test
CMP	3 mL	Light-green tube	UF Health	CRC	Visit 1
CBC and ESR	3 mL	Purple tube	UF Health	CRC	Visit 1
Total Immunoglobulins	3 mL	Light-green tube	UF Health	CRC	Visit 1 & 2
Pneumovax Serotypes	5 mL	Gold Tube	Mayo Clinic	CRC	Visit 1 & 2
Cytokines and inflammatory markers (i.e. IL-6, IL-12, IL-4, etc.)	15 mL	Gold Tube	[name] Lab	CRC	Visit 1 & 2
Antibody titers: IgG (isotypes); IgG1, IgG2, IgG3, IgG4, and					

IgM.					
Genetic testing to further assess immune response (ie STING genotyping analysis etc.) and future inflammatory analysis	10 mL	Purple Tube	[name] Lab	CRC	Visit 1 & 2
Total Blood Drawn	Visit 1: 39 mL	Visit 2: 33mL			
A1C	finger-prick		CRC	CRC	Visit 1
Hcg Pregnancy Test	20-50 mL	Urine Collection Cup	CRC	CRC	Visit 1

C. Data Storage and Confidentiality

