To test the primary hypothesis, we will use the Mayo criteria for positivity of 23 titers, with the primary outcome being the number of positives. We shall employ a two-sided ANCOVA, adjusting for age and gender to compare the obese cases to the non-obese controls. Secondarily, we will compare the 23 individual quantitative titers by similar ANCOVA analyses. Other endpoints will be analyzed in a similar manner as tertiary outcomes.

D. Randomization

No randomization will be done in this study.

E. Sample Size

We expect that 23 evaluable obese participants and 23 evaluable normal weight participants will complete the study. To accommodate for 20% attrition rate we will recruit 28 obese participants and 28 normal participants for a total of 56 eligible subjects. Additionally, to accommodate for individuals unable to participate due to exclusion criteria or individuals eliminated post-enrollment due to screening failure (e.g., CBC/CMP abnormalities), we plan to screen an additional 30 subjects. This accounts for a total of 86 individuals screened. Using information from the 2013-2014 MD-PhD study, we compared those with BMI <25 vs. those with BMI > 25. The distribution of Positive titers amongst the 14 was as follows:

BMI	5	6	7	8	9	10	11	12	Total
<25	1	2	0	2	2	1	4	2	14
>25	0	2	3	0	1	1	0	0	7

This should be viewed as conservative, as we will have greater separation of BMI values than the prior study. The actual gain in power cannot be quantified.

F. Technical Support

Under a CTSI voucher, [name] assisted with the statistics and data analysis. [name] co-authored the statistical section with the students. We will use CTRB facilities for blood draw, temporary tissue storage, and basic lab protocols. The laboratory of [name], MD, will be used to perform experimental procedures including the ELISA assays for IgG quantification.

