The primary outcome measure for the power calculation was the number of positive pneumococcal titers using data from Wildes et al. (2019). This study included a range of BMIs under 30. By comparing the number of positive titers between those with a BMI < 25 and > 25, we expect that 23 evaluable obese participants and 23 evaluable normal weight participants will provide enough power for the study (see the distribution of positive titers below in Table 1) at a significance level of $\alpha = 0.05$ for a 2-sided t test at 80% power. We consider this estimation to be conservative, as we expect that having a greater separation of BMI values than Wildes et al. will provide greater power. The actual gain in power cannot be quantified.

Table 1. The distribution of positive titers amongst the 14 in Wildes et al. study was as follows:

BMI	5	6	7	8	9	10	11	12	Total
<25	1	2	0	2	2	1	4	2	14

>25	0	2	3	0	1	1	0	0	7
-----	---	---	---	---	---	---	---	---	---

Aims and objectives

The aim of this project is to investigate the effect of obesity on the immune system's ability to mount a protective immune response against the pneumococcal polysaccharide vaccine (Pneumovax 23).

Outcomes

Primary outcome: Vaccine response as measured by serotype-specific IgG antibody responses against the 23 pneumococcal serotypes (i.e., 1, 2, 3, 4, 5, 6B, 7F, 8, 9N, 9V, 10A, 11A, 12F, 14, 15B, 17F, 18C, 19A, 19F, 20, 22F, 23F, 33F)

Statistics:

When comparing between populations (ie. baseline characteristics table), normality was first assessed by the Shapiro-Wilk test, then followed by either an unpaired 2-sided t test or a Wilcoxon's signed-rank test for parametric data or nonparametric data, respectively. Chi-square tests determined differences in categorical data (i.e. sex, ethnicity). For our primary analysis, we will use an ANCOVA to test for differences in fold change titer levels across groups (nonobese and obese), controlling for sex and age. All hypothesis tests were 2-sided where a P value < 0.05 was considered significant.

To assess the role of the STING genotype, a secondary analysis will be done using 2-way ANOVA of the fold change in titer levels between the wildtype, R232/R232, and HAQ carrier genotypes. Likewise, to assess the role of psychosocial variables, we will also be using an ANOVA or regression, as appropriate. For secondary analyses, we will not perform any multiple testing corrections for P values.

References

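### A null ELISA comparison between groups is the only stated trigger for a second assay of the non-primary serum analytes, and neither document says which assay's result counts

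*Protocol*

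**What the plan says.** Protocol 4.B (Measurements to be Collected), item 6, fixes the first-line method: "ELISA will be used to measure various acute phase reactants (e.g. TNF, C reactive protein, interferons, interleukins, etc.) and Ig subclasses". The next sentence, which runs across a page break, says that if significant "differences are not observed between arms then a cytometric bead assay may be employed". It gives no technical reason for the change, such as a detection limit, a failed run or sample volume. Neither document mentions a bead assay anywhere else.

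The analytes serve Specific Aim 2 and the secondary null hypothesis in Protocol section 2: "Levels of pro- and anti-inflammatory cytokine levels pre- and post-vaccination in individuals with a BMI between 22 and 25 and obese individuals are identical". Protocol Table 1 lists the samples ("Cytokines and inflammatory markers (i.e. IL-6, IL-12, IL-4, etc".), together with IgG1 to IgG4 and IgM, but names no assay. On analysis, Protocol 5.C says only: "Other endpoints will be analyzed in a similar manner as tertiary outcomes".

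The SAP sets the threshold: "All hypothesis tests were 2-sided where a P value < 0.05 was considered significant". It also states: "For secondary analyses, we will not perform any multiple testing corrections for P values". It does not mention cytokines, CRP, ELISA or the bead assay.

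The serotype-specific IgG titers, which carry the primary outcome, fall under item 5 and "will be analyzed using a panel ordered through the Mayo Clinic". Item 6 does not govern them.

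**The concern.** The rule works in one direction. A significant ELISA difference stands, while a non-significant one opens the way to another measurement. Choosing the assay after seeing the group comparison gives the null hypothesis two chances to be rejected, and a nominal 5% test is then no longer a 5% test.

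Three things are left open: whether the trigger is a null result for one analyte or for the whole panel, whether the bead assay re-measures the same analytes or adds new ones, and which result is tested and reported when both exist. At stake is how to read a significant cytokine, acute-phase or Ig-subclass difference if it comes from the bead assay.

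**Working it through.** **Scope.** The documents give no figure for this rule beyond the nominal 0.05. The stated 23 per group comes from the positive-titer table and reproduces: means 9.21 (n=14) and 7.43 (n=7), difference 1.79, pooled SD 2.10, and 80.4% power at 23 per group by the noncentral t. No ELISA analyte enters that calculation, so the sample size is unaffected.

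**Inputs.**
- Two-sided alpha 0.05 (SAP, Statistics), critical value 1.96.
- r, the correlation between the ELISA and bead test statistics under the null: assumed 0.8 to 0.95. The documents give none. High values are reasonable because both assays would use samples from the same participants.
- k, the number of analytes: assumed 5 to 20. The lists are open-ended. Ten can be counted by name (TNF, CRP, IL-6, IL-12, IL-4, IgG1–4, IgM), with interferons and interleukins also named as classes.
- The same analytes are re-measured, a significant result on either assay may count, and the bead assay is run whenever the trigger is met. None of this is stated.

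**Per-analyte trigger.** The error rate is e(r) = P(|Z1| > 1.96 or |Z2| > 1.96) for a standard bivariate normal with correlation r:
- r = 0.95: e = 0.0646
- r = 0.8: e = 0.0781

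**Panel-wide trigger.** The bead assay is run only if all k ELISA tests are null. A given analyte is falsely positive if its own ELISA is significant (0.05), or if its ELISA is null, its bead test is significant and the other k − 1 ELISAs are null. For independent analytes:

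error = 0.05 + (e − 0.05) × 0.95^(k−1)

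The multiplier 0.95^(k−1) is 0.815, 0.630 and 0.377 for k = 5, 10 and 20. The excess e − 0.05 is 0.0146 at r = 0.95 and 0.0281 at r = 0.8.

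| Trigger | r = 0.95 | r = 0.8 |
|---|---|---|
| Per analyte | 6.5% | 7.8% |
| Panel-wide, k = 5 | 6.2% | 7.3% |
| Panel-wide, k = 10 | 5.9% | 6.8% |
| Panel-wide, k = 20 | 5.5% | 6.1% |

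The range is therefore about 5.5% to 7.8%.

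**Checks.** Simulated ANCOVA with 23 per group, adjusting for age and sex (46 − 4 = 42 residual df), with k = 10 independent analytes, gave 5.9% and 6.8% for the panel-wide trigger and 6.5% and 7.9% for the per-analyte trigger. Correlating the analytes at 0.6 (assumed) gave panel-wide values of 5.7% and 6.7%. If the option is taken up after only half of the null panels, the excess halves: at k = 10, 5.5% and 5.9%.

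**Other readings.** If the bead assay measures only new analytes, each is tested once at 5%; what is added is a set of unadjusted tests prompted by a null result. If bead results are only shown beside ELISA, with ELISA still the result that counts, nothing is inflated.

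**The case against.** The strongest reply is that the harm is conditional. The wording is permissive. It does not say that the same analytes are re-measured or that a significant bead result displaces a null ELISA. Per-analyte error rises under only one of three readings. This stands: the documents establish a result-dependent trigger with no reporting rule, not an inflated error rate.

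It is also fair that no confirmatory claim is at risk. Protocol 5.C treats the other endpoints as tertiary, Protocol 4.E calls the study a pilot, and the contingency is disclosed. That lowers the priority but does not settle which result counts.

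The SAP's waiver of multiplicity correction does not answer the point either. It follows the STING and psychosocial analyses, in a document that never mentions these analytes, so applying it to them is an inference. Even if it applies, it concerns adjustment across tests, not the choice between two measurements of one analyte.

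A reader might infer more than the documents support:
- *That the primary result is compromised.* Protocol 4.F loosely describes the primary outcome as differences in immune-marker levels. The primary hypothesis, Protocol 5.C and the SAP all place it on pneumococcal titers, measured on a separate panel.
- *That the error rate nearly doubles.* The 9.75% figure (1 − 0.95²) needs two uncorrelated tests, which is implausible with samples from the same participants.
- *That the rule causes a panel-wide error near 40%.* With 10 independent analytes, 1 − 0.95^10 = 40.1% arises from ELISA alone, and the plan promises no panel-wide rate.

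**Conclusion.** The point holds in a limited form. Item 6 makes use of a second assay depend on the group comparison, and neither document names the result that counts. If the same analytes are re-tested and a significant bead result may count, the per-analyte false-positive rate is about 5.5%–7.8% instead of 5%. This rests on assumed values for the correlation (0.8 to 0.95) and the number of analytes (5 to 20), independent analytes under the panel-wide trigger, and use of the bead assay whenever triggered; less frequent use brings the rate closer to 5%. Under the other two readings the per-analyte rate stays at 5%. Only non-primary serum analytes are concerned, so this is a low-priority clarification.

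**What to change.** Replace the bead-assay sentence in Protocol 4.B item 6 with:

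> ELISA is the assay of record for these analytes. A cytometric bead assay may be used in its place only on assay-performance grounds (for example, values below the detection limit), decided without reference to study group and before any between-group comparison. Any other bead assay results are exploratory and are reported beside the ELISA results whatever either shows.

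This still allows a bead assay after a null ELISA, but only as a labelled, fully reported addition that cannot replace it. The cost is three sentences in place of one. Visits, blood volumes, sample size and primary analysis do not change. The sponsor gives up the option to switch assay because ELISA showed no group difference.
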